2.1 PRIMARY OBJECTIVE

• To assess the safety, tolerability, and efficacy of 12 weeks of SOF/VEL/VOX in subjects with chronic HCV infection who have previously failed FDA approved DAA-based therapy, with compensated cirrhosis and without cirrhosis, with and without HIV coinfection.

2.2 SECONDARY OBJECTIVES

- To evaluate the immunologic, virologic, and host genetic/proteomic predictors of response to therapy with SOF/VEL/VOX in HCV infected subjects who have failed previous combination DAA-based therapy
- To compare HCV quasispecies and resistance associated variants (RAVs) from baseline and throughout treatment, especially in the case of relapse or breakthrough, and assess the influence of past DAA experience on evolution of RAVs and on virologic response to treatment.
- To determine the kinetics of plasma HCV RNA during treatment and after treatment discontinuation.
- To evaluate the effect of SOF/VEL/VOX on peripheral markers of T cell activation.
- To evaluate the proportion of subjects whose alanine aminotransferase (ALT) levels normalize between baseline and SVR_{4,12,24}.
- To delineate the precise effects of specific HCV lifecycle inhibitors on host immune recovery in patients receiving single (SPARE), or combination DA therapy (RESOLVE).

2.3 EXPLORATORY OBJECTIVES

- Characterize immunologic, virologic, and host genetic/proteomic predictors of response
- Viral kinetic investigations, including early viral kinetics, resistance associated variants, HCV quasispecies
- To determine the impact of liver cirrhosis in SVR when treated with potent combination DAA therapy
- To delineate the precise effects of specific HCV lifecycle inhibitors on host immune recovery in patients receiving combination DAA therapy
- To compare the immunophenotypic responses of patients receiving SOF/VEL/VOX who have previously failed double and triple DAA therapy.
- 2.3.1 Rationale for Immunologic studies

We propose to study the B and T cell immune responses most associated with chronic HCV eradication after DAA therapy, in order to more fully understand the utility of new ultra short duration therapies for those chronically infected with HCV. We will define T cell immune responses associated with protective immunity in chronic HCV infection and further advance our understanding about host immunity that is associated with SVR. Studies on

B and T cell responses in HCV or HCV/HIV dual infection and the relationships to treatment outcomes require large numbers of patients and extensive clinical trials of DAA therapy. Our research team is making a major impact on the clinical understanding of DAA. We have collected and maintain a large specimen repository that is sufficient for our initial characterization of B and T cells and how they are related to protective immunity.

Chronic HCV infection is characterized by dysfunction of the adaptive immune system. DAA therapy is successful in resolving HCV infection and provides cure in up to 99% cases, except for late stage disease. Whether cure is associated with reconstituted immune regulation and what role the adaptive immune system plays in viral clearance is not known. Faster resolution of secondary infection after spontaneous clearance of HCV in humans and in chimpanzees points to a role for immunological memory in HCV control. Defining the immune correlates of DAA mediated sustained virologic response will help understand the immune defects that may be associated with treatment failure.

Hypothesis

[figure not shown]
Hypothesis #1: Augmentation of HCV specific cellular immune responses with DAA therapy is associated with SVR.

Hypothesis #2: Healthy (non cirrhotic) liver is critical in mounting HCV specific cellular immunity in DAA treated patients

Hypothesis #3: Specific inhibition of stages of HCV lifecycle leads to precise immune recovery in chronic HCV infected patients treated with combination DAA therapy.

[figure not shown]
Study Design and Analysis

To achieve these objectives, we will analyze peripheral and intrahepatic cellular immunity in patients who are cirrhotic and those who are not, as described in detail below. The responses/changes observed over time with DAA therapy will be compared between the two groups to evaluate first objective.

To address the second objective, we will utilize samples collected from previous studies that used either single DAA (SPARE), dual or multiple DAA therapy (present study) to determine the

differential effect of specific HCV lifecycle inhibitors (NS5B alone, NS5B with NS5A and NS5B with NS5A and NS5B with NS5A and NS3 inhibitors). The assays that will characterize peripheral and intrahepatic cellular immunity are described in detail below. The changes from baseline to the end of therapy (or full viral suppression) will be compared in all patients receiving various regimens to determine the differential effect of added suppression of NS5A and or NS3.

2.4 STUDY POPULATION

It is anticipated that approximately 150 HCV infected subjects, including screening failures and drop-outs, will be screened for this study. The target population is chronic HCV patients who are treatment-experienced with combination DAA therapy and failed to achieve SVR₁₂ in the United States. This study is designed to target an understudied demographic of the HCV epidemic in the United States in which current therapy has had poor results. There will be no racial, ethnic, religious, or gender discrimination. Persons in jail or prison are not eligible for this study. We will be enrolling participants from ongoing clinical trials with collaborators, as well as recruiting referrals. Healthy adults will be recruited through Institutional Review Board (IRB)-approved advertising to HCV providers and screened to confirm eligibility requirements for participation.

The following eligibility criteria will be used:

2.4.1 Inclusion Criteria

A subject must meet all of the following criteria:

- 1. At least 18 years of age or older at screening.
- 2. Available for clinical follow-up through Week 44 after enrollment.

- 3. Recurrent HCV GT-1 infection as documented by ≥ 1 measurement of serum HCV RNA ≥ 1,000 IUM/mL during screening and documented history of receiving prior HCV treatment.
- 4. Exposure to combination DAA therapy, including, but not limited to, the following regimens:
 - a. $LDV/SOF \pm RBV$
 - b. Viekira Pak \pm RBV
 - c. $EBR/GZR \pm RBV$
- 5. Ability to communicate effectively with the study investigator and other key personnel.
- 6. Opioid-dependent individuals must be participating in a supervised treatment program or considered stable at the discretion of the investigator.
- 7. Subjects must have a primary care doctor for their medical management.
- 8. Able and willing to complete the informed consent process.
- 9. Willing to donate blood for sample storage to be used for future research.
- 10. Female study participants with childbearing potential (as defined below) and all male study participants must be willing to practice either:
- Complete abstinence from sexual intercourse with a member of the opposite sex **OR**
- At least one form of effective contraception from the list below, in addition to correct use of either a male or female condom with spermicide, throughout dosing and for a defined period following the last dose (30 days for women, 14 days for men) of study medication.:
 - i. Intrauterine device with a failure rate of <1% per year
 - ii. Tubal sterilization
 - iii. Bilateral tubal occlusion
 - iv. Vasectomy in a male partner
 - v. Female barrier method (diaphragm or cervical cap) with spermicide
 - vi. Hormonal methods
 - 1. Oral contraceptives
 - 2. Injectable progesterone
 - 3. Implants of levonorgestrel or etonorgestrel
 - 4. Transdermal contraceptive patch
 - 5. Contraceptive vaginal ring
- 11. Hepatitis B coinfected participants, must have evidence of chronic infection and controlled on treatment.
- 12. HIV coinfected participants only must have HIV status of one of the following:
 - a. HIV untreated for ≥ 8 weeks prior to Screening

- i. CD4 T-cell count >500 cells/mm³ at Screening
- ii. No intention of initiating ARV therapy for the duration of trial

OR

- b. HIV suppressed on a stable, protocol-approved, ARV regimen for \geq 4 weeks prior to Screening
 - i. Completed at least 3 months of any prior HIV ARV therapy and maintained HIV RNA < 50 copies/mL (or < LLOQ if the local laboratory assay's LLOQ is ≥50 copies/mL) prior to Screening. Subjects with an isolated or unconfirmed HIV RNA > 50 copies/mL (or > LLOQ if the local laboratory assay's LLOQ is ≥50 copies/mL) are not excluded.
 - ii. CD4 count >100 cells/mm3 at Screening
 - iii. HIV antiretroviral (ARV) agents allowed in this study include
 - FTC/TAF [Descovy®], FTC/TDF [Truvada®], or ABC/3TC [Epzicom®]

plus

- Ritonavir (r) and darunavir (DRV), OR
- Raltegravir (RAL), OR
- Elvitegravir (EVG) ± Cobicistat (c), or
- Rilpivirine (RPV)

Or

Fixed dose combinations as below

- FTC/RPV/TAF [Odefsey®]
- FTC/RPV/TDF [Complera®]
- EVG/c/TAF/FTC [Genvoya®]
- EVG/c/TDF/FTC [Stribild®]

Alternative ARV regimens will be considered on an individual basis, based on available DDI data at the discretion of the principal investigator

iv. The subject is expected to continue the current ARV regimen for the duration of the trial

Cirrhosis Criteria:

13. Liver fibrosis staging as determined by an AASLD/IDSA guideline-approved Page 23 of 55 measurement, within three years of Screening, including any one of the following:

- a. Imaging
- b. Liver biopsy
- c. Transient elastography
- d. Noninvasive markers

Liver imaging within 6 months of Day 0 to exclude hepatocellular carcinoma (HCC) is required in patients with cirrhosis.

2.4.2 Exclusion Criteria

A subject will be excluded if one or more of the following conditions apply:

- 1. Combination DAA therapy was completed or discontinued less than 8 weeks prior to enrollment.
- 2. Current or prior history of any of the following:
 - a. Clinically significant illness (other than HCV) or any other major medical disorder that may, in the opinion of the investigator, interfere with the subject treatment, assessment of compliance with the protocol; subjects currently under evaluation for a clinically-significant illness (other than HCV) are also excluded
 - b. Gastrointestinal disorder with post-operative condition that could interfere with the absorption of the study drugs
 - c. Poor venous access interfering with required study blood collection
 - d. Hepatic impairment or decompensation (e.g., Child-Pugh class B [moderate] or Child-Pugh class C [severe])
 - e. Solid organ transplantation
 - f. Significant pulmonary disease, significant cardiac disease, or porphyria.
 - g. Unstable psychiatric disease, including hospitalization, suicide attempt, and/or a period of disability as a result of their psychiatric illness within 2 years prior to Screening (subjects with psychiatric illness that is well-controlled on a stable treatment regimen or currently not requiring medication may be included)
 - h. Any malignancy or its treatment that in the opinion of the PI may cause ongoing interference with host immunity; subjects under evaluation for malignancy are not eligible
 - i. Chronic liver disease of a non-HCV etiology (e.g., hemochromatosis, Wilson's disease, alfa-1 antitrypsin deficiency, cholangitis)
- 3. Abnormal hematological and biochemical parameters at screening, unless the test has been repeated and at least one subsequent result is within the acceptable range prior to study drug administration, including:
 - a. Neutrophil count <750 cells/mm³
 - b. Hemoglobin level <10 g/dL
 - c. Platelet count \leq 50,000 cells/mm³
 - d. Estimated glomerular filtration rate, calculated by the chronic kidney disease epidemiology collaboration formula: <30 mL/min/1.73 m²
 - e. ALT or AST level ≥ 10 times upper limit of normal (ULN)
 - f. Serum lipase level ≥1.5 times ULN at screening or during the screening period in a patient with symptoms of pancreatitis

- g. Total bilirubin level \geq 2.0 times ULN, except in subjects with Gilbert's syndrome or other clinical explanation at the discretion of the PI.
- h. Albumin level <3 g/dL
- 4. Poorly controlled diabetes as indicated by a screening glycosylated hemoglobin (HbA1c) >10
- 5. Known hypersensitivity to any of the study medications
- 6. Screening ECG with clinically significant findings
- 7. Need for the use of the following medications from 21 days prior to the start of study drugs through the end of treatment:
 - a. Hematologic stimulating agents, erythropoiesis stimulating agents (ESAs), granulocyte colony stimulating factor (GCSF), thrombopoeitin (TPO) mimetics
 - b. Chronic systemic antineoplastic or immunomodulatory treatment including supraphysiologic doses of immunosuppressants such as corticosteroids (e.g., prednisone equivalent >10 mg/day for >2 weeks), azathioprine or monoclonal antibodies (e.g., infliximab)
 - c. Investigational agents or devices for any indication
 - d. Use of certain medications and herbal/natural supplements per PI discretion, expected to result in increases or decreases in exposure to study or non-study medications as listed in section 3.5 (Table 3-1).
- 8. Any medical, psychiatric, social condition, occupational reason or other responsibility that, in the judgment of the investigator, is a contraindication to protocol participation or impairs a volunteer's ability to give informed consent.

Female-specific criteria:

9. Woman who is breast-feeding or planning to become pregnant during the first 24 weeks after study drug administration.

2.5 PHARMACOKINETIC AND VIRAL KINETIC SUBSTUDY

Participants, N=20 (10 participants with cirrhosis and 10 without cirrhosis) that meet the above criteria and who are willing to participate will be eligible for a voluntary 24 hour and 72 hour pharmacokinetic (PK) and viral kinetic (VK) substudy.

2.6 RECRUITMENT PLAN

The study will be advertised and posted using flyers. All advertisements will be IRB approved before use.

2.7 HUMAN SUBJECTS PROTECTIONS

Subjects will be fully counseled prior to entry into the study as to the potential risks of the study and consenting using good clinical practice. Subjects who, in the opinion of the study team, do

not fully comprehend these potential risks will not be offered participation in the study. Subjects will be monitored closely during their participation in the study.

2.7.1 Gender, Ethnicity, and Race Considerations

Subjects will not be excluded based on gender. This study is designed to target an underrepresented demographic of the HCV epidemic in the United States with poor representation in clinical trials, and in which current therapy has had poor results.

2.7.2 Rationale for the Exclusion of Children and Pregnant Women

This study will be limited to adults aged 18 years or older. Insufficient data are available to evaluate the safety and efficacy of SOF, VEL and VOX in the pediatric population. The risks of SOF or VEL or VOX during pregnancy have not been evaluated; therefore, pregnant or nursing women will be excluded from this study. Any woman of child-bearing potential must have a negative pregnancy test on Day 0 prior to receiving the first dose of SOF/VEL/VOX and use effective contraception throughout the study.

2.7.3 Contraception

Male subjects, as well as female subjects who are potentially capable of becoming pregnant, will be required to use at least 2 forms of contraception, one method must be correct use of a condom with spermicide, from 2 weeks prior to Day 0 until after completing study drug (30 days post completion for women, 14 days for men following the last dose of study drug. Female partners of male study subjects may rely upon hormonal contraceptives as one of the 2 forms, however female study subjects may not. As study drugs are investigational agents, prevention of pregnancy, in a subject or partner, during and after treatment is important as the risks are as yet unknown.

Definitions:

a. Definition of Childbearing Potential: For the purposes of this study, a female born subject is considered of childbearing potential from menarche until becoming post-menopausal, unless permanently sterile or with medically documented ovarian failure.

Women are considered to be in a post-menopausal state when they are ≥ 54 years of age with cessation of previously occurring menses for ≥ 12 months without an alternative cause. Permanent sterilization includes hysterectomy, bilateral oophorectomy, or bilateral salpingectomy in a female subject of any age.

b. Definition of Male Fertility: For the purposes of this study, a male born subject is considered of fertile after the initiation of puberty unless permanently sterile by bilateral orchiectomy or medical documentation.

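### Inclusion criterion 10 accepts hormonal contraception as a female subject's second method, but section 2.7.3 does not let her count it

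*Combined protocol and SAP*

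**What the plan says.** Criterion 10 in section 2.4.1 covers both sexes in one sentence: "Female study participants with childbearing potential (as defined below) and all male study participants must be willing to practice either". It then offers two routes. The first is "Complete abstinence from sexual intercourse with a member of the opposite sex". The second is "At least one form of effective contraception from the list below, in addition to correct use of either a male or female condom with spermicide", to be kept up "throughout dosing and for a defined period following the last dose (30 days for women, 14 days for men) of study medication". The list that follows has six headings, the last of which is "vi. Hormonal methods" with five sub-types (oral, injectable, implant, patch, ring). No entry under that heading is limited by sex.

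Section 2.7.3 sets the conduct rule for male subjects and for women who could become pregnant. It asks for at least two forms, one being a condom with spermicide, "from 2 weeks prior to Day 0 until after completing study drug", and ends at the same 30 days (women) or 14 days (men) after the last dose. On hormonal methods it states: "Female partners of male study subjects may rely upon hormonal contraceptives as one of the 2 forms, however female study subjects may not". It does not mention abstinence.

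Section 2.7.2, in a paragraph explaining why pregnant women are excluded, says that women of childbearing potential must "use effective contraception throughout the study".

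**The concern.** Eligibility is decided at screening by reviewing the inclusion and exclusion criteria (section 2.8.1). If that list accepts a combination of methods that the contraception section rejects, the trial can enrol a woman who is out of compliance from the outset without anyone having misread the criterion. The foreseeable results are inconsistent counselling and avoidable protocol deviations.

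The protocol itself treats pregnancy prevention as important. Section 2.7.2 says that the risks in pregnancy have not been evaluated, and section 3.4.2 makes pregnancy a reason to stop all study medication. Female subjects and site staff should not have to choose between two rules on this.

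**Working it through.** No power, alpha or rate is involved. The check compares the two sections line by line and then looks for a rule elsewhere that settles the difference.

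| Item | Criterion 10 (2.4.1) | Section 2.7.3 | Relation |
|---|---|---|---|
| Forms when contraception is used | One listed method plus condom with spermicide | Two, one a condom with spermicide | Agree |
| Hormonal method as a female subject's second form | Accepted | Not accepted | Contradict |
| Start | Dosing | 2 weeks before Day 0 | 2.7.3 adds a requirement |
| End | 30 days (women), 14 days (men) after last dose | Same | Agree |
| Abstinence | Accepted as an alternative | Not mentioned | Gap |

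**Methods.** Take a woman of childbearing potential who uses an oral contraceptive and a condom with spermicide.
- Under criterion 10 she has one listed method plus the condom, so she qualifies.
- Under 2.7.3 the oral contraceptive does not count, so she has one counted form where two are required.
- The bar removes one of six headings, or five of the ten named methods (i to v make five; vi.1 to vi.5 make five).

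**Start.** Twelve weeks of dosing is 12 × 7 = 84 days.
- Women: criterion 10 covers 84 + 30 = 114 days; 2.7.3 covers 14 + 84 + 30 = 128 days.
- Men: 84 + 14 = 98 days against 14 + 84 + 14 = 112 days.
- The difference is 14 days in each case, all of it before Day 0. Following 2.7.3 satisfies both sections.

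**Abstinence.** Criterion 10 makes it an explicit alternative. Read literally, 2.7.3's two-form requirement leaves no place for it, but the section says nothing against it.

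**Is there a reconciling rule?** None was found.
- Criterion 10 sends the reader onward only for the definition of childbearing potential. That definition is in 2.7.3, but criterion 10 does not refer to 2.7.3 for methods.
- Section 2.7.2 is general wording in a rationale paragraph and does not address methods.
- Exclusion 9 concerns breast-feeding and planned pregnancy.
- Table 3-1 in section 3.5 lists seven drug classes, none of them hormonal contraceptives. The protocol calls the entries examples, so their absence settles nothing.
- No statement gives one section precedence over the other.

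**Safeguards already in place.** Section 2.11 requires a history and a negative pregnancy test before the first dose. Section 5.1 repeats the test every 4 weeks on treatment, so the next is at about Week 4, that is day 28 ± 3, or 25 to 31 daily doses. Section 2.10 provides for a review of study restrictions and questions on adherence to them, although it does not name contraception. These limit the risk but do not say which rule applies.

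**The case against.** The strongest reply is that criterion 10 is a general list and 2.7.3 is the specific rule. The list pools methods for both sexes (a partner's vasectomy can apply only to female subjects), and criterion 10 tests willingness whereas 2.7.3 governs conduct. A site that follows the stricter section breaks neither. Study staff from one institution attend all scheduled and unscheduled visits (section 2.8), so opposite advice from different teams is less likely than in a large multicentre trial.

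Part of this stands. There is a workable reading, and the lead-in is an added requirement that can be met alongside criterion 10. It does not dispose of the methods point: the protocol never says that the stricter section prevails, and the same staff would hold both rules.

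A second objection also stands: the documents do not show which rule was intended. Section 2.7.3 gives no specific reason for the hormonal bar. Its general justification is that the drugs are investigational with unknown risks, while section 1.6.3 records FDA approval of the combination. The remedy should therefore leave the choice to the sponsor.

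A reader might infer three direct contradictions. The text supports only one: the start is an addition and abstinence is an omission. A reader might also infer that the bar reflects a known drug interaction, or that these women would be unprotected. The documents give no such reason for the bar, and the woman in the example is still using two methods, one of which 2.7.3 declines to count.

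**Conclusion.** The inconsistency is real. On hormonal methods for female subjects, criterion 10 and 2.7.3 give opposite answers, and screening is checked against the more permissive text. The 14-day difference in start and the silence on abstinence are lesser mismatches to tidy at the same time, and the wording in 2.7.2 is merely loose.

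This is a minor safety and eligibility correction that should be made. The documents do not say how many women of childbearing potential are expected, so no rate of affected subjects or of pregnancies can be given. No harm to male subjects is suggested. Sample size, power and the SVR12 analysis are untouched. The conclusion rests only on the wording of the two sections and on finding no reconciling text. The consent pages are not in this copy, so what subjects were told cannot be judged.

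**What to change.** State one rule in both places.

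- **Criterion 10, by default:** limit item vi to female partners of male subjects, so that female subjects choose their second form from items i to v. Start the window 2 weeks before Day 0 and keep the existing ends.
- **Section 2.7.3:** name complete abstinence as an alternative to the two forms.
- **Section 2.7.2:** replace the general phrase about duration with a reference to 2.7.3.
- **Alternative:** if the sponsor confirms that hormonal methods are acceptable for female subjects, delete the bar from 2.7.3 and leave item vi as it is.

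The default follows the stricter text until the sponsor decides.

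The cost is wording, with no added visits or tests. Under the default, women on hormonal methods need another listed method or abstinence, as 2.7.3 already implies. A subject not yet compliant may start up to 2 weeks later; screening may open up to 8 weeks before dosing, so this can often be absorbed. Consent wording should be checked for consistency.
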